Aim 2. Evaluate the preliminary efficacy of ACTivate in improving physical function and other outcomes in HCT patients (NIH Stage IB). As standard of care, all HCT patients undergo comprehensive functional evaluation (physical, cognitive, mental health, nutrition, social/financial, global, and quality of life) between sign-off (~10 days before HCT) and year 3. This will allow us to compare outcomes in the nine patients in Aim 1 plus an expansion cohort of 11 patients receiving the final iteration of ACTivate (total n=20) to contemporaneous controls matched for age, gender, and disease.

H1: Patients receiving ACTivate will have a shorter hospital stay and better physical function (six-minute walk, primary endpoint) at year 3.

3. **Background and Significance**

Allogeneic hematopoietic stem cell transplant (HCT) has the potential to cure patients with hematologic malignancies and other diseases, but treatment is arduous and there is significant risk of treatment-related morbidity and mortality. Worse clinical outcomes are predicted not only by advanced chronological age, but also by modifiable behavioral factors such as decreased physical function and comorbid psychological conditions, such as depression. Targeted interventions to reduce physical and psychological vulnerabilities during the pre-HCT time period could therefore improve treatment tolerance and HCT outcomes.

ACT [1] is a transdiagnostic, mindfulness-based treatment that has been effective in reducing psychological distress and symptom interference in a variety of clinical populations [2-5], including individuals with cancer [6-15]. Unlike more traditional cognitive-behavioral therapy (CBT), which focuses on changing thoughts/feelings themselves, ACT emphasizes psychological acceptance: voluntarily adopting an open, receptive posture with respect to moment-to-moment experience. This may be well-matched to individuals with cancer for whom distressing thoughts/feelings may not be illogical or irrational, but rather perfectly normal or expected responses to having a life-threatening illness (and embarking on a journey that could cure their disease but could also cause death), or simply inevitable during the course of treatment.

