Significance. The curative potential of HCT is balanced by the significant risk of treatment-related morbidity, and mortality ranges from 10-30% [23-25]. Outcomes are worse in patients of advanced age, decreased physical function, and depressed mood [26-29]. Targeted interventions that reduce physical and psychological vulnerabilities pre-HCT have the potential to increase treatment tolerance and dramatically change illness trajectories and maintain long-term mobility and quality of life post-HCT, particularly for older adults. ACT is a newer CBT that has significant potential for this purpose [4]. ACT has decreased psychological distress and symptom interference and produced behavior change in a variety of clinical populations, including individuals with depression, anxiety, disordered eating, diabetes, and chronic pain [2-5]. Unlike traditional CBT, which focuses on correcting cognitive distortions, the target mechanism in ACT is psychological flexibility (the ability to allow experience to be what it is and move in the direction of values) [16]. Increased psychological flexibility may help HCT patients accept their situation (and the distressing thoughts/feelings that arise) and direct their attention to how they want to live the moments of their lives and to the things they can control.

For example, chemotherapy/radiation creates adverse interoceptive signaling (nausea, pain, fatigue) that may elicit maladaptive behavioral response patterns in HCT patients (sedentary behavior, disengagement, suboptimal nutritional intake). Individuals must actively choose to override these signals and engage in behaviors that may briefly intensify uncomfortable experiences in the service of improving treatment outcomes (walking, drinking protein shakes). Through ACT, individuals may better accept the discomfort associated with HCT and adapt behaviors in ways that improve function and survival. Further, the infusion of personal values in ACT may increase patient motivation to engage in health behaviors, even in the face of uncertain outcomes.

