Table 1. Assessments	Baseline	Every 2 Weeks	Continuous from Baseline	Day 30, Day 90, Day 180, Year 1, Year 2, Year 3
Physical function				
6-minute walk	X			X
Short physical performance battery	X			X
30 second sit-stand	X			X

Protocol Summary of: Pro00105683

Step count (activity tracker data)			X	
Falls question	X			X
PROMIS Fatigue*	X			X
PROMIS Physical Function*	X			X
Cognitive function				
Montreal Cognitive Assessment	X			X
PROMIS Cognitive Function*	X			X
Emotional / Psychological				
PHQ-9 (Depression)**	X			X
Valuing Questionnaire (VQ)*	X	X		
PC-PTSD/PCL**	X			X
PROMIS Depression**	X			X
PROMIS Anxiety**	X			X
PROMIS Emotional Support**	X			X
PROMIS Social Isolation**	X			X
HHI-12*	X			X
Brief COPE*	X			X
AAQ-II*	X			X
Nutrition				
Albumin	X			X
Body-mass index			X	
PONS	X			X
Clinician SGA	X			X
PG-SGA*	X			X
ASA-24*	X			X
Social/financial				
CMS Social determinants of health	X			X
FACIT-COST	X			X
Sociodemographics**	X			
SES (caregiver only)*	X			X (only Day 180, year 1, 2, 3)
Financial Assessment	X			X
Global				
Fried Frailty	X			X
OARS IADLs	X			X
Quality of life				
FACT BMT	X			X
FACT GP (caregiver only)*	X			X
EQ-5D-5L	X			X
Lorig Self Efficacy *	X			X
Self-Efficacy Preparedness for Caregivers (caregiver only)*	X			X
Miscellaneous				
PROMIS Global Health*	X			X

Protocol Summary of: Pro00105683

PROMIS Sleep*	X			X
HCT-CI (completed by MD)	X			
Clinical outcomes				
Adverse events (e.g., graft-host disease)			X	
Resource utilization (e.g., length of hospital stay)			X	
Symptoms				
PRO-CTCAE core symptoms*	Weekly through year 1			
Sample collections				
Stool**	X			X + Day 0, 7, 14, 21, 60
Skin**	X			X
Blood*	X			X + Day 14
Treatment development				
Acceptability survey**	X			X (only during ACT session time points as listed above)
Exit Interviews**				X
Note: Measures not collected as part of routine care are marked with an *. Measures marked with ** are assessments taken by caregivers too. All year 3 biosample collections will be optional.				

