Measures. Measures are outlined in Table 1. The majority of the assessments are collected as part of routine HCT procedures or tracked in the Duke Adult Bone Marrow Transplant (ABMT) database. Assessments that are not typically collected during HCT procedures have been marked with an (*). Primary outcomes will be the 6-minute walk and length of hospital stay. Target engagement (process of change) will be assessed with the Valuing Questionnaire (VQ) (or equivalent), administered to the patient and the caregiver every 2 weeks for the first 30 days, and once a month thereafter.

ACTivate sessions will be conducted in person or via the Duke extended care platform used for telehealth visits. Participants will also receive reminders of concepts from sessions and reinforcement or prompting from the study team via the custom HCT app (e.g., “Great job completing your steps yesterday!”). All sessions will be audio taped for fidelity review. Fidelity will be assessed with the ACT Measure (ACT-FM), along with an ACTivate protocol checklist (developed after finalization of the protocol in Aim 1). Session tapes from the second interventionist will be reviewed by [name] for ongoing training/consultation to maintain fidelity to the intervention.

Participants’ functional outcomes at Day 30 and Day 90 will be compared to age, gender, and disease-matched controls (case-control design), collected as standard of care.

Use of previously collected data: If a subject is simultaneously on another study and the same assessment or sample is required for both studies, we will only collect once and share the data between studies to avoid subjects having to duplicate efforts.

5. Selection of Subjects

Protocol Summary of: Pro00105683

Eligibility criteria: (1) Over the age of 18 (2) undergoing allogeneic HCT for any cancer or non-cancer illness, (3) English-speaking (4) has a caregiver who is willing to participate. Caregiver eligibility criteria: (1) Over the age of 18 and (2) English-speaking.

6. Subject Recruitment and Compensation

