Relationship of Risks to Benefits: This is a low risk intervention study that does not involve the use of a study drug or investigational device. No adverse health effects had been established from the use of the iPhone or Apple Watch. There is risk of loss of confidentiality, as with any study, and with studies with mobile devices. Treatment-related morbidity is high among HCT patients and mortality ranges from 10-30%. The potential benefit of interventions to increase treatment tolerance is thus substantial. Given the minimal risks associated with the study methods, the risk-benefit analysis is highly favorable.

10. Costs to the Subject

There are no direct costs to subjects.

11. Data Analysis & Statistical Considerations

Study variables will be described using summary statistics and graphical methods. Continuous variables (e.g., 6 minute walk (primary endpoint), AAQ2) will use the generalized linear model with the outcome of interest at year 3 as the dependent variable and treatment assignment as the primary predictor of interest, with a priori selected covariates age, gender, and disease. Ordered categorical outcomes (e.g. Fried Frailty) will use ordered logistic regression models in the same form above. Other outcomes (e.g., length of stay) will be assessed using an adaptation of the Cox regression model [35]. Primary analyses will be followed by examining the extent to which engagement is associated with outcomes using appropriate modeling. We also will explore the trajectory of outcome changes using generalized linear repeated measures models. We will carefully examine model assumptions (e.g., residuals, linearity, influential cases) and reparameterize models accordingly. Assuming an alpha of 0.05 and 10% attrition at 90 days, for the continuous outcomes, a sample size of 60 (20:40) will afford 80% power to detect a standardized group difference of just over 0.8 SDs. This translates to about a 16 meter treatment group difference in the six minute walk test.

12. Data & Safety monitoring

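### HCT-CI is a routine baseline item but enters neither the matching nor any model, and the length-of-stay model names no covariates, so a systematic comorbidity difference would be credited to ACTivate

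*Combined protocol and SAP*

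**What the plan says.** **Controls.** Section 2, Aim 2, uses "contemporaneous controls matched for age, gender, and disease". Section 4 (Measures) says that functional outcomes at Day 30 and Day 90 will be "compared to age, gender, and disease-matched controls (case-control design), collected as standard of care". Section 6 assigns every recruit to the intervention and calls the control group historical.

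**Entry.** Section 5 admits any allogeneic transplant, whatever the indication, and requires a caregiver who will take part. Section 6 refers patients to research staff if they express interest. Neither condition is stated for controls.

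**Models.** Section 11 fits continuous outcomes "with a priori selected covariates age, gender, and disease", and ordered outcomes in the same form. Length of stay gets an adapted Cox model with no covariates named. Section 4 lists length of stay as a primary outcome beside the six-minute walk; Aim 2 and Section 11 attach the primary label to the walk alone.

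**Comorbidity.** Table 1 lists "HCT-CI (completed by MD" at baseline, without the asterisk that marks items outside routine care. It appears in no analysis.

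**Conditioning.** It is mentioned in Section 4 only to time samples. Its intensity is not in Table 1, the matching or the models.

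**The concern.** Without randomisation, only the matching and the covariates stand between a difference in case mix and an apparent treatment effect. Here both use the same three variables, so the model adds little protection against anything the matching left open. Patients of the same age, gender and disease can differ in comorbidity. Those who volunteer and bring a caregiver may differ systematically from those who do not, and if the controls are historical, the case mix may also have shifted over time.

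The gap is widest for length of stay, where the protocol does not commit even to the three variables used elsewhere. Section 11 offers no propensity score and no sensitivity analysis for confounding. Its checks of residuals, linearity and influential cases do not address the problem. At stake is whether the Aim 2 efficacy signal can be interpreted. A comorbidity difference in one direction would look like benefit; in the other it could hide a benefit.

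**Working it through.** **1. The plan's own figure.** Section 11 gives the inputs: "Assuming an alpha of 0.05 and 10% attrition at 90 days, for the continuous outcomes", and then "a sample size of 60 (20:40) will afford 80% power to detect a standardized group difference of just over 0.8 SDs". Sidedness is not stated, so two-sided is assumed. Ten per cent attrition turns 20:40 into 18:36.

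- Standard error of the difference, in SD units: √(1/18 + 1/36) = 0.2887.
- Normal approximation: (1.960 + 0.842) × 0.2887 = 0.809 SD.
- Noncentral t, 52 degrees of freedom: 0.824 SD; power at 0.82 SD is 79.6%.

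The figure reproduces, so the sample size is not in dispute. The calculation assumes an unadjusted comparison free of bias.

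**2. What an omitted factor could do.** The documents give neither the imbalance nor the prognostic strength, so both are assumed. Bias (in outcome SD) = imbalance in the factor (SD) × effect on outcome per SD of the factor. Dividing the bias by 0.2887 gives the noncentrality; the two-sided rejection rate at 52 degrees of freedom follows, with ACTivate having no effect.

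| Imbalance | Effect per SD | Bias | False-positive rate |
|---|---|---|---|
| 0.2 SD | 0.2 to 0.5 | 0.04 to 0.10 SD | 5.2 to 6.3% |
| 0.5 SD | 0.2 to 0.5 | 0.10 to 0.25 SD | 6.3 to 13.6% |
| 0.8 SD | 0.2 to 0.5 | 0.16 to 0.40 SD | 8.5 to 27.5% |

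For the middle row: 0.10 / 0.2887 = 0.35 and 0.25 / 0.2887 = 0.87. Section 11 equates its detectable difference with 16 metres, which implies an SD of 19 to 20 metres (16/0.824 = 19.4; 16/0.8 = 20). A bias of 0.10 to 0.25 SD is then about 2 to 5 metres. The calculation is for a continuous outcome such as the walk. It is not a calculation for the length-of-stay model, for which the documents give no design figures.

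**3. What adjustment costs.** At 18:36, counting disease as one degree of freedom:

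- Three covariates, explaining nothing: 0.825 SD detectable.
- Five covariates (HCT-CI and conditioning added), explaining nothing: 0.826 SD.
- Five covariates explaining 10%, 20% or 30% of outcome variance: 0.783, 0.739 or 0.691 SD.
- If an added factor is itself imbalanced by d SD, the variance of the group effect grows by about 1 + d² × (1/3) × (2/3). For d = 0.5: √1.056 × 0.826 = 0.85 SD. For d = 0.8: √1.142 × 0.826 = 0.88 SD.

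The degrees of freedom cost almost nothing. Precision suffers only where the factor is badly imbalanced, which is also where adjustment matters most.

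**The case against.** **No imbalance is shown, and every driver of its size is assumed.** This stands. Matching on age and disease may absorb part of any difference, and at the low end the false-positive rate barely moves from 5%.

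**The protocol does not establish that these factors predict the outcomes.** This also stands, in part. The Significance text in Section 3 names older age, poorer physical function and low mood as predictors of worse outcome, not comorbidity. On treatment it says that "chemotherapy/radiation creates adverse interoceptive signaling (nausea, pain, fatigue) that may elicit maladaptive behavioral response patterns in HCT patients". A reader might infer that conditioning intensity acts directly on length of stay and belongs at the centre of the point. The documents do not support that: the sentence says may, does not mention intensity, and does not mention length of stay. Conditioning is therefore a secondary suggestion.

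**Chance imbalance.** A reader might also argue that a factor with 50% prevalence has a chance imbalance of SD √(0.25 × (1/20 + 1/40)) = 0.137 between 20 and 40 patients, or about ±27 points, and that an assumed effect of 5 to 10 days would shift the stay difference by 1.3 to 2.7 days. That is random error, already in the standard error and the confidence interval. It does not raise the false-positive rate and is no measure of bias. Only a systematic difference does that.

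**Availability.** HCT-CI for controls is inferred from its routine-care status. Conditioning is not a listed variable, and the chart abstraction in Section 4 refers to the study's own subjects.

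**This is a pilot of preliminary efficacy.** True, and it limits the weight of the point. But Section 11 already commits to a priori covariates and a significance level, so naming one more collected variable is proportionate.

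**Fewer patients at year 3.** The cost above uses 90-day attrition, while Section 11 models the walk at year 3 and Section 3 cites 10 to 30% mortality. Disease may also take several degrees of freedom. Both would reduce precision below the figures shown.

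**Conclusion.** The point holds as a risk of confounding that the plan could cheaply reduce. Matching and adjustment use only age, gender and disease, the length-of-stay model names no covariates, and a routine baseline comorbidity item is left unused. With an assumed 0.5 SD imbalance and 0.2 to 0.5 SD of outcome per SD of the factor, the false-positive rate would be about 6 to 14% against a nominal 5%. Across all the assumed inputs it runs from 5.2 to 27.5%.

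It would go too far to conclude that the comparison is biased, or that a conditioning difference will be read as an ACTivate effect. The documents show no imbalance and no direction. The weight of the point rests on the non-randomised, self-selected comparison and on HCT-CI being available for controls.

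**What to change.** In Section 11, add baseline HCT-CI as an a priori covariate in the six-minute-walk and length-of-stay models, and state that the length-of-stay model also carries age, gender and disease.

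Confirm that HCT-CI is on record for the controls. If conditioning intensity can be taken from transplant records for both groups (an assumption), add it as a two-level covariate or in a sensitivity analysis. Report HCT-CI and, where available, conditioning by group.

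The cost is a sentence or two of text and one or two degrees of freedom (0.825 to 0.826 SD detectable at 18:36). If an added factor is imbalanced by 0.5 to 0.8 SD, the detectable difference rises to about 0.85 to 0.88 SD. The adjustment does not remove selection through volunteering or having a caregiver; that limitation should be stated with the results.

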We will recruit 20 adults around HCT workup (when patients undergo medical testing and commit to HCT). To be eligible, participants must be ≥ 18 years old ($n=10 < 60$ years, $n=10 \geq 60$ years), English speaking and receiving allogeneic HCT. They must also have a caregiver who is willing to participate. This age range is selected because the Duke Adult Blood and Marrow Transplant Program only cares for adults ≥ 18 years, and because we want to evaluate the impact in older and younger patients, we plan to recruit 10 < 60 years and 10 ≥ 60 years. Patients and their caregivers will complete a 1-6 session ACT protocol tailored to the clinical challenges of HCT. Assessments (outlined in Table 1) will be administered at key points to assess target engagement (process of change) and treatment outcomes. Self-report measures will be administered via a secure online survey tool (REDCap). Please see appendix A for REDCap survey distribution details. The caregiver will participate in the baseline and exit interviews, complete the acceptability measures, psychological assessments (with themselves as the identified person), and stool and skin collection. All other measures will only be completed by the patient. Patients will also use a custom HCT mobile application (or app) -- either Technology Recordings to better Understand BMT (TRU-BMT) (used in our previous studies (Pro00068979 and Pro00092963)) or SplendoFit -- to report things such as symptoms, diet and exercise, and wear an activity tracker (Apple Watch) during the intervention. Step data will be passively transmitted to the treatment team daily from the Apple Watch. We do not expect that there will be technical difficulty with the use of TRU-BMT or SplendoFit apps. The TRU-BMT app has already been piloted in Duke HCT patients (Pro00068979, PI [name], co-I [name]) and was rated favorably as both easy to use and helpful (abstract presentation at the American Society of Hematology 2017 Annual Meeting).

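### The language and caregiver entry criteria apply to ACTivate patients but not to controls, so caregiver availability and language are potential uncontrolled confounders of the efficacy comparison.

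*Combined protocol and SAP*

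**What the plan says.** **Treated group.** Section 5 lists the patient criteria, including "3) English-speaking (4) has a caregiver who is willing to participate". Section 4 repeats the requirement: "They must also have a caregiver who is willing to participate". The caregiver must qualify as well: "Caregiver eligibility criteria: (1) Over the age of 18 and (2) English-speaking". Sections 6 and 8 assign every recruited participant to the intervention, so there is no randomisation.

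**Controls.** Aim 2 in Section 2 compares the 20 ACTivate patients with "contemporaneous controls matched for age, gender, and disease". Section 4 (Measures) says that functional outcomes at Day 30 and Day 90 "will be compared to age, gender, and disease-matched controls (case-control design), collected as standard of care". Neither place, nor any other, applies the language or caregiver criterion to controls.

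**Model.** Section 11 fits a generalised linear model to the six-minute walk at year 3, "with a priori selected covariates age, gender, and disease". Length of stay uses an adaptation of Cox regression.

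**Data available on controls.** By the note to Table 1, measures without an asterisk are routine care. HCT-CI and the CMS Social determinants of health measure carry none. Both are collected at baseline, and neither is used for matching or adjustment.

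**Decliners.** Section 7 says that people who are screened and do not consent are not recorded.

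**The concern.** Matching makes groups comparable only on the factors matched. Here the treated group passes two further filters, language and a willing caregiver, and the control group as described passes neither. The model reuses the three matching factors, so nothing later in the plan removes a difference that the filters might create.

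The caregiver filter matters because a patient who already has an available caregiver may do better around a transplant admission, with or without ACT. If so, and if some controls lack such a person, part of any advantage in the walk or in length of stay would be wrongly credited to ACTivate. Because decliners are not recorded, selection among those approached cannot be described afterwards. The control rule therefore has to be settled before controls are chosen.

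**Working it through.** **1. Setting the rules side by side**

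| Factor | ACTivate patients | Controls | Section 11 model |
|---|---|---|---|
| Age, gender, disease | recorded | matched | adjusted |
| English-speaking | required | not mentioned | not adjusted |
| Willing caregiver | required | not mentioned | not adjusted |
| HCT-CI | recorded at baseline | routine care by the Table 1 note | not adjusted |

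A control who could not have entered the treated group is admissible as the plan stands.

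**2. Reproducing the plan's own figure**

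Inputs from Section 11: 60 patients (20:40), alpha 0.05, 10% attrition at 90 days, 80% power. Two-sided testing is assumed because the plan does not say.

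- Evaluable: 20 × 0.9 = 18 and 40 × 0.9 = 36.
- Standard error of the difference: √(1/18 + 1/36) = 0.289 SD.
- Detectable difference: (1.960 + 0.842) × 0.289 = 0.809 SD by the normal formula, 0.824 SD by the t-test.

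This agrees with the plan's figure of just over 0.8 SD. The stated 16 m implies an SD of about 16/0.8 = 20 m. The power statement is sound; the issue is comparability.

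**3. What a given bias would do**

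Suppose ACT has no effect and selection alone favours the treated group by b SD on the walk. The rejection probability comes from a noncentral t distribution with noncentrality b/SE, two-sided 5%, both tails counted. The values of b are assumptions.

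| Assumed bias b | 18 v 36 (SE 0.289) | 14 v 28 (SE 0.327) |
|---|---|---|
| 0 | 5% | 5% |
| 0.2 SD | 10.4% | 9% |
| 0.3 SD | 17.5% | 15% |
| 0.4 SD | 27.5% | 22% |

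The first column of results uses the plan's 90-day attrition. The second assumes 30% loss by year 3 (20 × 0.7 = 14, 40 × 0.7 = 28), since Section 11 models the year 3 outcome but gives no attrition figure for it. Both concern the walk only, not the Cox analysis of length of stay.

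**4. What would have to be true to reach such a bias**

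Let q be the share of controls with a comparable caregiver and g the effect of having one, in SD. All treated patients have one, so b = (1 − q) × g. Neither q nor g is in the documents; the ranges are assumed. Rates are normal approximations at 18 v 36.

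| q | g | b (SD) | Metres at SD 20 m | False-positive rate |
|---|---|---|---|---|
| 100% | any | 0 | 0 | 5.0% |
| 90% | 0.25–0.8 | 0.03–0.08 | 0.5–1.6 | 5.1–5.9% |
| 70% | 0.25–0.8 | 0.08–0.24 | 1.5–4.8 | 5.8–13.2% |
| 50% | 0.25–0.8 | 0.13–0.40 | 2.5–8.0 | 7.2–28.3% |

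With g no larger than 0.8 SD, a bias of 0.4 SD needs half the controls to be without a caregiver and a caregiver effect equal to the plan's whole target difference. If nine controls in ten have one, the effect on the error rate is slight.

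**The case against.** **No imbalance is shown.** A reader might infer that the treated group is in fact better supported than the controls. The documents do not support that: nothing says how many controls lack a caregiver or do not speak English. This stands, and it limits the point to a factor left uncontrolled.

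**The caregiver is part of the treatment.** Section 3 mostly describes the caregiver's role inside ACTivate, as a coach who practises the same skills. Its remark on the value of including a caregiver concerns other populations. It does not say that merely having a caregiver improves the walk or shortens the stay. This stands against reading Section 3 as an admission of confounding. It does not remove the point, because an available and willing caregiver is a characteristic the patient has before the first session, separate from the coaching.

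**Comorbidity.** A reader might also infer that treated patients are less ill. Section 5 sets no comorbidity or performance limit, and nothing links language or caregiver status to HCT-CI. The inference is unsupported. What remains is only that a routinely recorded prognostic score goes unused.

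**It is a pilot.** Residual selection is unavoidable in a 20-patient, non-randomised Stage IB study. That is so, but Aim 2 states a directional hypothesis and Section 11 gives it a model, an alpha and a power. Aligning the recordable criteria is a cheap reduction in bias.

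**Conclusion.** The point holds as a matter of uncontrolled potential confounding. It rests on the text: two entry criteria restrict the treated group, no stated rule applies them to controls, and matching and adjustment cover only age, gender and disease.

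Its size is unknown. Bias from caregiver availability is nil if all controls have comparable caregivers. The rates of about 10%, 18% and 27% (about 9%, 15% and 22% at the assumed year 3 numbers) follow only if the assumed biases of 0.2, 0.3 and 0.4 SD are granted, and they apply to the walk alone. The control rule should be changed before controls are selected, but the documents do not show that the comparison is already biased.

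**What to change.** 1. In Aim 2 (Section 2) and Measures (Section 4), state that the control pool is limited to patients who meet the same recordable criteria as treated patients: adult, allogeneic HCT, English-speaking, and an identified caregiver where the chart records one. Apply this before matching on age, gender and disease.
2. The documents do not confirm that caregiver status is charted. If it is not, use the baseline CMS Social determinants of health measure as a proxy covariate, and say that it is a proxy.
3. In Section 11, add baseline HCT-CI as a covariate, described as a general prognostic adjustment.
4. Report the balance between groups on language, caregiver status or its proxy, and HCT-CI.
5. State that the willingness of patient and caregiver to volunteer cannot be matched, since an identified caregiver is not the same as a willing one, and that this limits the efficacy conclusion.
6. Reconcile Aim 2, which calls the controls contemporaneous, with Section 6, which calls them historical. This affects which data can be obtained for them.

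The cost is protocol wording, chart screening of candidate controls, a smaller control pool and possibly looser matches. The added covariates use a few degrees of freedom in a sample of 60. No visits or patients are added.
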